2.1.1. Primary Estimand(s)

None.

2.1.2. Secondary Estimand(s)

None.

2.1.3. Additional Estimand(s)

None.

2.2. Study Design

This is a Phase 1, randomized, double-blind, sponsor-open, placebo-controlled, oral dosing study of PF-06882961 in adult Chinese participants with T2DM inadequately controlled on diet, exercise and metformin background therapy.

Participants will receive oral doses of PF-06882961 or placebo in this study. Approximately 20 participants will be randomized to PF-06882961 or placebo at a 3:1 ratio (15 participants

to PF-06882961 and 5 participants to placebo) such that at least 8 participants in PF-06882961 group will complete 120 mg and be evaluable for PK analysis. The study will be conducted at a single clinical site in China.

The target dose level is PF-06882961 120 mg BID (or matching placebo). Following the screening period to confirm eligibility (up to 4 weeks), the treatment period will be approximately 8 weeks, followed by an approximate 4-week follow-up. The dose of PF-06882961 will be increased following a prespecified titration scheme during visits V2 through V8 to reach the target dose, which will then be maintained through V10. Downward titration or dosing is not permitted during the study. Participants who do not tolerate the titration scheme and/or assigned dose may be required to discontinue dosing of study intervention. See **Figure 1** and **Figure 2** for schema of the design and dose titration.

Figure 1. Schema of Study

➤ Day 1 QD; Day 2-56 BID

[figure not shown]
[figure not shown]

Figure 2. Dose Titration Scheme

3. ENDPOINTS AND BASELINE VARIABLES: DEFINITIONS AND CONVENTIONS

3.1. Primary Endpoint(s)

The primary endpoints of the study are

- Single dose (10 mg): Area under the plasma concentration-time profile from time zero to 24 hours (AUC_{24}), maximum observed concentration observed from time zero to 24 hours (C_{max}) collected at Day 1.
- Multiple dose (40 mg, 80 mg, 120 mg): AUC_{24} , $C_{max,ss}$ collected at steady state.

3.2. Secondary Endpoint(s)

The secondary endpoints of the study are safety endpoints including vital signs, electrocardiograms, adverse events (e.g. hypoglycemia and hyperglycemia), clinical safety laboratory assessments.

More details of the safety endpoint are described in Section 3.5.

CC1

The PK parameters (primary endpoints CCI [REDACTED]) for PF-06882961 will be calculated from the concentration-time data using non-compartmental methods. Definition and method of determination are described in **Table 2** below.

Table 2. Definition of Plasma PK Parameters for PF-06882961

Parameter	Day 1 (D1) or Steady State (SS)	Definition	Method of Determination
C_{\max}	D1 & SS	Maximum observed concentration observed from time zero to 24 hours	Observed directly from data
$C_{\max1}$ and $C_{\max2}$	D1 & SS	$C_{\max1}$: maximum plasma concentration during the dosing interval $\tau_1 = 0$ to 10 hours $C_{\max2}$: maximum plasma concentration during the dosing interval $\tau_2 = 10$ to 24 hours	Observed directly from data
$C_{\max1}$ (dn), $C_{\max2}$ (dn) and C_{\max} (dn)	D1 & SS	$C_{\max1}$, $C_{\max2}$ and C_{\max} normalized to a 1 mg dose.	$C_{\max1}/\text{Dose}$ $C_{\max2}/\text{Dose}$ C_{\max}/Dose
CCI			
AUC_{τ_1} and AUC_{τ_2}	SS	Area under the plasma concentration-time profile from time zero to time τ , where $\tau_1 = 0$ to 10 hours and $\tau_2 = 10$ to 24 hours	Linear/Log trapezoidal method
AUC_{τ_1} (dn) and AUC_{τ_2} (dn)	SS	AUC_{τ_1} and AUC_{τ_2} normalized to a 1 mg dose	AUC_{τ_1}/Dose AUC_{τ_2}/Dose
AUC_{24}	D1	Area under the plasma concentration-time profile from time zero to time 24 hours	Linear/Log trapezoidal method
AUC_{24}	SS	Area under the plasma concentration-time profile from time zero to time 24 hours	$AUC_{\tau_1} + AUC_{\tau_2}$
AUC_{24} (dn)	D1 & SS	AUC_{24} normalized to a 1 mg dose.	$AUC_{24}/\text{Total Daily Dose}$
CCI			

Table 2. Definition of Plasma PK Parameters for PF-06882961

Parameter	Day 1 (D1) or Steady State (SS)	Definition	Method of Determination
			CCI [REDACTED]
			CCI [REDACTED]
CCI			

D1=Day 1. SS=Steady Status. dn= Dose Normalized value.

CCI [REDACTED]
 CCI [REDACTED]

3.4. Baseline Variables

Baseline variables include age, gender, race, ethnicity, height, weight, body mass index, duration of diabetes, CCI [REDACTED]. Baseline variables for vital sign and ECG data are described in [Section 6.6.3](#) and [Section 6.6.4](#). Baseline variables are those collected on Day -1 or last measurement during screening visits before Day 1.

The duration of diabetes will the time from primary diagnosis date to the randomization date into this study.

3.5. Safety Endpoints

3.5.1. Adverse Events (AEs)

An adverse event is considered a Treatment-Emergent Adverse Event (TEAE) if the event started during the effective duration of treatment.

All events that start on or after the first dosing day and time/start time, if collected, but before the last dose plus the lag time will be flagged as TEAEs. If an AE starts on the same day as the first dose date, it will be considered treatment emergent unless the case report form data indicates otherwise via explicitly recording time for AE onset and treatment dosing.

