### **8.3.1. Time Period and Frequency for Collecting AE and SAE Information**

The time period for actively eliciting and collecting AEs and SAEs (“active collection period”) for each participant begins from the time the participant provides informed consent, which is obtained before the participant’s participation in the study (ie, before undergoing any study-related procedure and/or receiving study intervention), through and including a minimum of 28 calendar days, after the last administration of the study intervention.

Follow-up by the investigator continues throughout and after the active collection period and until the AE or SAE or its sequelae resolve or stabilize at a level acceptable to the investigator and Pfizer concurs with that assessment.

For participants who are screen failures, the active collection period ends when screen failure status is determined.

If the participant withdraws from the study and also withdraws consent for the collection of future information, the active collection period ends when consent is withdrawn.

If a participant definitively discontinues or temporarily discontinues study intervention because of an AE or SAE, the AE or SAE must be recorded on the CRF and the SAE reported using the CT SAE Report Form.

Investigators are not obligated to actively seek AEs or SAEs after the participant has concluded study participation. However, if the investigator learns of any SAE, including a death, at any time after a participant has completed the study, and he/she considers the event to be reasonably related to the study intervention, the investigator must promptly report the SAE to Pfizer using the CT SAE Report Form.

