### 10.3. Appendix 3: Adverse Events: Definitions and Procedures for Recording, Evaluating, Follow-up, and Reporting

#### 10.3.1. Definition of AE

AE Definition

• An AE is any untoward medical occurrence in a patient or clinical study participant, temporally associated with the use of study intervention, whether or not considered related to the study intervention.

• NOTE: An AE can therefore be any unfavorable and unintended sign (including an abnormal laboratory finding), symptom, or disease (new or exacerbated) temporally associated with the use of study intervention.

Events Meeting the AE Definition

• Any abnormal laboratory test results (hematology, clinical chemistry, or urinalysis) or other safety assessments (eg, ECG, radiological scans, vital sign measurements), including those that worsen from baseline, considered clinically significant in the medical and scientific judgment of the investigator. Any abnormal laboratory test results that meet any of the conditions below must be recorded as an AE:

• Is associated with accompanying symptoms.

• Requires additional diagnostic testing or medical/surgical intervention.

• Leads to a change in study dosing (outside of any protocol-specified dose adjustments) or discontinuation from the study, significant additional concomitant drug treatment, or other therapy.

• Exacerbation of a chronic or intermittent preexisting condition including either an increase in frequency and/or intensity of the condition.

• New conditions detected or diagnosed after study intervention administration even though it may have been present before the start of the study.

• Signs, symptoms, or the clinical sequelae of a suspected drug-drug interaction.

• Signs, symptoms, or the clinical sequelae of a suspected overdose of either study intervention or a concomitant medication. Overdose per se will not be reported as an AE/SAE unless it is an intentional overdose taken with possible suicidal/self-harming intent. Such overdoses should be reported regardless of sequelae.

Events NOT Meeting the AE Definition

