### Assessment of Intensity

The investigator will make an assessment of intensity for each AE and SAE reported during the study and assign it to 1 of the following categories:

- Mild: An event that is easily tolerated by the participant, causing minimal discomfort and not interfering with everyday activities.
- Moderate: An event that causes sufficient discomfort and interferes with normal everyday activities.
- Severe: An event that prevents normal everyday activities. An AE that is assessed as severe should not be confused with an SAE. Severe is a category utilized for rating the intensity of an event; and both AEs and SAEs can be assessed as severe.
- An event is defined as “serious” when it meets at least 1 of the predefined outcomes as described in the definition of an SAE, NOT when it is rated as severe.

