#### **Follow-up of AEs and SAEs**

- The investigator is obligated to perform or arrange for the conduct of supplemental measurements and/or evaluations as medically indicated or as requested by the sponsor to elucidate the nature and/or causality of the AE or SAE as fully as possible. This may include additional laboratory tests or investigations, histopathological examinations, or consultation with other healthcare providers.
- If a participant dies during participation in the study or during a recognized follow-up period, the investigator will provide Pfizer Safety with a copy of any postmortem findings including histopathology.
- New or updated information will be recorded in the originally completed CRF.
- The investigator will submit any updated SAE data to the sponsor within 24 hours of receipt of the information.

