6.6.1. Adverse Events

Adverse events will be reported in accordance with the CaPS by treatment group and dose level.

Besides the standard incidence and severity of TEAE summaries, the number of TEAEs (all causality and treatment related) by severity, System Organ Class, and Preferred Term will also be produced.

The hypoglycemic AEs will be listed in a separate table and summarized categorically (See Section 3.5.1.1) by treatment and dose level.

CCI

CCI

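### The SAP flags a TEAE by start date alone, so an AE first recorded between consent and first dose that worsens on treatment can be left out of the TEAE tables

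*SAP*

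**What the plan says.** SAP 3.5.1 defines treatment emergence by onset: "An adverse event is considered a Treatment-Emergent Adverse Event (TEAE) if the event started during the effective duration of treatment". The sentence that follows turns this into a programming rule. Events starting at or after the first dose "but before the last dose plus the lag time will be flagged as TEAEs". Both sentences look only at when the event started.

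The protocol sets how AEs are collected and recorded:

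- Section 8.3.1: the active collection period "for each participant begins from the time the participant provides informed consent".
- Section 10.3.3, on grading: "The investigator will make an assessment of intensity for each AE and SAE reported during the study and assign it to 1 of the following". The three grades are mild, moderate and severe.
- Section 10.3.3, on follow-up: "New or updated information will be recorded in the originally completed CRF".
- Section 10.3.1 lists among the events that are AEs: "Exacerbation of a chronic or intermittent preexisting condition including either an increase in frequency and/or intensity of the condition".

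SAP 6.6.1 then sets the reporting: "Adverse events will be reported in accordance with the CaPS by treatment group and dose level". Besides the standard incidence and severity tables, it adds counts of TEAEs by severity, system organ class and preferred term.

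**The concern.** Safety and tolerability form the secondary objective, and AEs are a secondary endpoint. A symptom that was mild before dosing and becomes moderate or severe on study drug is evidence on tolerability, and the protocol's own AE definition recognises increased intensity. Under the SAP rule, whether that evidence reaches a TEAE table depends on the start date in the CRF row. If the site updates the existing row, the start date stays before the first dose, and the event drops out of the incidence, severity and event-count tables together.

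For these events the omission can only lower TEAE counts. With 15 participants planned on active and 5 on placebo, a single omission is visible in a percentage table.

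**Working it through.** The plan states no figure to reproduce. The check is a reading of the rules against each other, plus the weight of one participant.

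**Can an AE row exist before the first dose?** Yes. Collection begins at consent. Protocol Table 1 places consent in Screening, Day -28 to Day -3, and schedules AE monitoring at Screening and on admission at Visit 2. With no Day 0 in the schedule, the interval from consent to first dosing on Day 1 is 3 to 28 days.

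**How does each kind of event fare under SAP 3.5.1?**

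| Course of the event | How the protocol has it recorded | Flagged as TEAE? |
|---|---|---|
| Medical-history condition that worsens after first dose | The exacerbation is an AE in its own right (10.3.1), with onset on treatment | Yes |
| Event that begins after first dose, at any dose level | New AE with onset on treatment | Yes |
| AE recorded between consent and first dose, still present, more intense after first dose; site opens a new row | New row with on-treatment start | Yes |
| Same course; site updates the existing row (10.3.3) | One row, one intensity, pre-dose start | No |

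Only the last row fails. The third and fourth rows describe the same clinical course, and neither document says which way it should be recorded. Section 10.3.1 can be read as supporting a new AE, and the follow-up text in 10.3.3 as supporting an update to the old one. The protocol does not say whether the single intensity is the one at onset or the worst reached. That does not matter for the flag, because SAP 3.5.1 never consults intensity.

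**What does one missed participant weigh?** Inputs: 15 on active and 5 on placebo (Protocol 9.2). The change in participant incidence is 1/n:

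- active: 1/15 = 0.067, or 6.7 percentage points
- placebo: 1/5 = 0.20, or 20 percentage points

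This applies to the incidence of a given term, and only if that participant has no other flagged event of the same term. The documents give no basis for estimating how many participants would be affected.

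**The case against.** The strongest reply is that the gap is small and its mechanism partly inferred. The follow-up text in Protocol 10.3.3 does not say in terms that a rise in intensity must stay in the same AE row, and the CRF completion guide is not among the documents. A guide that already required a new row would close the gap in practice. The tables are descriptive, no hypothesis is tested, and the primary PK endpoints do not depend on them. Protocol 4.2 plans comparisons with Studies C3421002 and C3421005, so a TEAE definition changed only here could make tolerability harder to compare. All of this stands as a limit on importance. It does not supply the missing clause: the SAP rule as written leaves the flag to a recording choice that the two documents do not settle.

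Two stronger readings are tempting. A reader might infer that every event present before dosing is lost. That is wrong, because a medical-history condition that worsens is a separate AE under 10.3.1 with onset on treatment. A reader might also infer that an event starting at a low dose and worsening at a higher one is missed, or credited to the wrong dose. It is not missed: it starts after the first dose and is a TEAE. Nor does a wrong dose assignment follow. SAP 3.5.1 sets no dose level, and SAP 6.6.1 defers to the sponsor's reporting standard (CaPS), which is not in the documents, with redacted text nearby. Assignment to the dose at onset, the dose at worst intensity, or every dose during which the event was present would all fit the visible text. At most, an attribution rule is not visible.

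**Conclusion.** The concern holds in a limited form. The start-date rule in SAP 3.5.1 can omit one class of event from the TEAE tables: an AE recorded after consent and before the first dose that increases in intensity on treatment and is kept in its existing row. Each such omission is worth up to 6.7 points on active or 20 points on placebo for the term concerned.

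This rests on two assumptions: that sites follow the 10.3.3 update instruction for such events, and that no unseen CRF guidance or sponsor standard overrides it. How often the situation will arise cannot be judged from the documents. The correction is worth making because it is cheap and because tolerability is a stated objective. The lack of a visible dose-attribution rule is a point to clarify, not an error shown.

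**What to change.** 1. In SAP 3.5.1, define a TEAE as an event that starts on or after the first dose, or that starts before the first dose and increases in intensity after it, within the same window as now.
2. In the CRF completion instructions, have such an increase recorded as a new AE row with its own start date, linked to the earlier row. The clause needs this: a single row with one intensity and no date of change cannot show that the increase came after dosing. The study has one site, so one instruction is enough.
3. Count linked rows once in participant incidence.
4. Report the onset-only count alongside, so that comparisons with the other studies do not depend on the change.
5. As a clarification, state in SAP 6.6.1 how an AE that spans titration steps is assigned to a dose level, or cite the part of the sponsor standard that says so.

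The cost is a few lines of SAP text, one CRF instruction and minor programming. The drawbacks are slightly more TEAE rows and a possible difference from the definition in the comparison studies, which item 4 handles. If AE data have already been collected, only rows with a pre-dose start that were ongoing at the first dose need checking before database release.

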3.5.1.1. Hypoglycemic Adverse Event (HAE)

Details of hypoglycemia AEs will be recorded in the Case Report Form (CRF) as a separate page. The definition and severity of categorization of HAE are described in the protocol Section 8.2.5.2.1.

For programming purposes, the hypoglycemic AE categories are based on the following:

- **Severe Hypoglycemia:** Severe is checked in the severity criteria of the CRF. This assessment will be made by the PI based on the protocol definition.
- **Documented Symptomatic Hypoglycemia:** If (1 – Did the subject have symptoms of hypoglycemia?) Yes and (2 – Was blood glucose measured?) Yes and result <70 mg/dL on the CRF, but hypoglycemia is not classified as severe.
- **Asymptomatic Hypoglycemia:** If (1) No and (2) Yes and result <70 mg/dL on the CRF, but hypoglycemia is not classified as severe.
- **Probable Symptomatic Hypoglycemia:** If (1) Yes and (2) No and (2b – If blood glucose was not measured, did symptoms resolve when treated with carbohydrate or glucagon?) Yes on the CRF, but hypoglycemia is not classified as severe.

3.5.2. Laboratory Data

Safety laboratory tests will be performed as described in the protocol.

To determine if there are any clinically significant laboratory abnormalities, the hematological, clinical chemistry, urinalysis, and other safety tests will be assessed against the criteria specified in the sponsor reporting standards.

Baseline will be the last predose measurement collected on Day -1.

3.5.2.1. Change from Baseline Summaries

Focused change from baseline summaries of the following safety laboratory endpoints will be assessed:

- Change from baseline in calcitonin to all post-dose time points as per the Schedule of activities (SoA) in the protocol .
- Change from baseline in amylase to all post-dose time points as per the SoA.
- Change from baseline in lipase to all post-dose time points as per the SoA.
- Change from baseline in thyroid stimulating hormone (TSH) to all post-dose time points as per the SoA.
- Change from baseline in free thyroxine (free T4) to all post-dose time points as per the SoA.
- Change from baseline in lipid profile (total cholesterol, direct LDL cholesterol, HDL cholesterol and triglycerides) to all post-dose time points as per the SoA.

- Change from baseline in liver function tests (ALT, AST, alkaline phosphatase, and total bilirubin) to all post-dose time points as per the SoA.

3.5.3. Vital Signs

Vital sign measurements (blood pressure and pulse rate) will be taken as detailed in the schedule of activities given in the protocol. The average of the triplicate measurements at each appropriate assessment time will be calculated for each blood pressure and pulse rate, if applicable.

Changes from time-matched baseline for supine systolic and diastolic blood pressure and pulse rate will be calculated for each post baseline measurement. Baseline is defined as the time-matched value from the average of the triplicate recordings on Day -1.

In addition, the time-matched double difference in supine blood pressures and pulse rate measurements is calculated in the following steps: (1) subtract predose value on Day 1 from all postdose values; (2) subtract the value at 0 hours on Day -1 from all other values on Day 1; (3) take the difference between the adjusted postdose value in (1) and its time-matched value in (2).

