**Table 2. Schedule of Activities – Study Days -1, 1, 21, 35 & 56**

[Procedures at 0H to be completed prior to dosing or similar clock time, in the case of Day-1]

Hours Relative to Dosing at 0H a	0	0.25	0.5	1	1.5	2	3	4	6	8	10	12	14	24
Continued inpatient stay at study site	→	→	→	→	→	→	→	→	→	→	→	→	→	→
Adverse event monitoring	→	→	→	→	→	→	→	→	→	→	→	→	→	→
Review prior and concomitant treatments	→	→	→	→	→	→	→	→	→	→	→	→	→	→
Review drug, alcohol, tobacco use	→	→	→	→	→	→	→	→	→	→	→	→	→	→
Review drug diary, glucometer & glucose diary b	x													
COVID-19 check temperature	x													
Glucose measurement (fasting, via glucometer)	x													
Triplicate, supine vital sign assessment c	x			x		x		x		x		x		
Triplicate, supine 12-lead ECG	x			x		x		x		x		x		
CCI	x													
Randomization in trial (Day 1 only)	x													
Dosing on site of IP with meal (Days 1, 21, 35, and 56 only)	x d										x e			
Standardized meal/snack f	x g							x			x		x	
Blood Sampling for:														
CCI	x													
Hematology, chemistry (inc. eGFR) (Days -1, 21, 35, 56 only)	x													
Lipids, TSH, free T4, calcitonin, amylase, lipase, TBA, PT/INR/aPTT (Days -1 and 56 only)	x													
PF-06882961 PK (Days 1, 21, 35, and 56 only)	x h			x		x		x	x	x	x	x	x	x
Urine Sampling for:														
Urinalysis (and microscopy, as appropriate) (Day -1 only)	x													
Blood or Urine Sampling for:														
Pregnancy test (for WOCBP only) (Days 21, 35, 56 only)	x													

- On Day -1, nominal time to match approximate clock time of collection planned on Day 1 to permit time matched comparison.
- Review glucometer and glucose diary only on Day -1.
- Includes blood pressure and pulse rate.
- Dosing expected to occur with breakfast or mixed meal. Day 1 only single dose at 0H
- Dosing expected to occur with dinner. No dosing at this timepoint on Day 1.
- Meals/snacks to occur on all days while inpatient; identical meals/snacks on Days -1, 1, 21, 35, and 56.
- Standard breakfast on Day 1 and all other inpatient days.
- Collection following fasting duration.

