### 8.2.3. Vital Signs

Supine BP will be measured with the participant's arm supported at the level of the heart, and recorded to the nearest mmHg after approximately 5 minutes of rest. The same arm (preferably the dominant arm) will be used throughout the study. Participants should be

instructed not to speak during measurements. When a meal or snack is scheduled at the same time as measuring BP and PR, the measuring BP and PR must be performed prior to the meal/snack. When triplicate BP and PR are required, they will be obtained approximately 2 to 4 minutes apart; the average of the triplicate BP and PR measurements collected at each nominal time point on Day -1 will serve as each participant's time-controlled baseline values.

The same properly sized and calibrated BP cuff will be used to measure BP each time. The use of an automated device for measuring BP and pulse rate is acceptable; however, when done manually, pulse rate will be measured in the brachial/radial artery for at least 30 seconds. When the timing of these measurements coincides with a blood collection, BP and pulse rate should be obtained prior to the nominal time of the blood collection.

Additional collection times, or changes to collection times, of BP and pulse rate will be permitted, as necessary, to ensure appropriate collection of safety data.

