3.5.4. Electrocardiograms

Standard 12-lead ECG (including heart rate, PR, QT, QTcF intervals and QRS complex) will be obtained at times detailed in the schedule of activities given in the protocol. The average of the triplicate readings collected at each appropriate assessment time will be calculated for each ECG parameter, if applicable.

Change from time-matched baseline for heart rate, PR, QT, QTcF intervals and QRS complex will be calculated for each post baseline measurement. Baseline is defined as the time-matched value from the average of the triplicate recordings on Day -1.

In addition, the time-matched double difference in heart rate, PR, QT, QTcF and QRS measures is calculated in the following steps: (1) subtract predose value on Day 1 from all postdose values; (2) subtract the value at 0 hours on Day -1 from all other values on Day -1; (3) take the difference between the adjusted postdose value in (1) and its time-matched value in (2).

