6.6.3. Vital Signs Data

Baseline values, absolute values and changes from time-matched baseline values in supine systolic, supine diastolic blood pressure and pulse rate will be summarized by treatment, time post-dose and day with descriptive statistics stated in Section 5.2.2 (according to CaPS). Tables will be paged by parameter. Baseline is as defined in Section 3.5.3.

Maximum absolute values and maximum changes from time-matched baseline for vital signs will also be summarized descriptively as stated in Section 5.2.3 using categories as defined in Appendix 1 (Section 9.1).

All planned and unplanned post dose time points will be counted in these categorical summaries. The time-matched double differences in vital signs obtained following the Day 1 treatment, as defined in [Section 3.5.3](#), will be summarized (N, mean, 90% confidence interval) for each treatment and time point.

Mean time-matched double differences in vital signs will be plotted against time post-dose for Day 1 and Day 56 separately. On each plot there will be 1 line for each treatment.

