6.6.4. ECG Data

Baseline values, absolute values and changes from time-matched baseline in QT, heart rate, QTcF interval, PR interval and QRS complex will be summarized by treatment and time post-dose and day with descriptive statistics stated in [Section 5.2.2](#) following CaPS. Tables will be paged by parameter. Baseline is as defined in [Section 3.5.4](#).

Maximum increase from time-matched baseline for QTcF and heart rate will be summarized by treatment, according to sponsor reporting standards.

The number (%) of participants with maximum absolute value and maximum increase from baseline for QTcF, PR and QRS (see Appendix 1 in [Section 9.1](#)) will be summarized using method stated in [Section 5.2.3](#).

All planned and unplanned post-dose time-points will be counted in these categorical summaries.

The time-matched double differences in QT interval, heart rate, QTcF interval, PR interval, and QRS complex measures obtained following the Day 1 treatment, as defined in [Section 3.5.4](#), will be summarized (N, mean, 90% confidence interval) for each treatment and time point.

6.6.5. Mean time-matched double differences in ECG parameters will be plotted against time postdose for Day 1 and Day 56 separately. On each plot there will be 1 line for each treatment. Physical Examination

Physical examinations will be summarized by treatment and dose level in accordance to CaPS.

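### Read as written, the Day 1 vital-sign double difference in SAP 3.5.3 cancels the postdose reading, because step (2) names Day 1 where the ECG rule names Day -1

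*SAP*

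**What the plan says.** SAP 3.5.3 defines the vital-sign double difference as follows:

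- Step (1): "subtract predose value on Day 1 from all postdose values".
- Step (2): "subtract the value at 0 hours on Day -1 from all other values on Day 1".
- Step (3): take the result of (1) minus the time-matched result of (2).

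SAP 3.5.4 sets out the same three steps for the ECG parameters, except that step (2) reads "subtract the value at 0 hours on Day -1 from all other values on Day -1".

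SAP 6.6.3 refers back to Section 3.5.3 for the definition. The Day 1 double differences "will be summarized (N, mean, 90% confidence interval) for each treatment and time point". It adds that "Mean time-matched double differences in vital signs will be plotted against time post-dose for Day 1 and Day 56 separately".

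The protocol explains what Day -1 is for. A footnote to Table 2 sets its "nominal time to match approximate clock time of collection planned on Day 1 to permit time matched comparison". Protocol 8.2.3 makes "the average of the triplicate BP and PR measurements collected at each nominal time point on Day -1" the participant's time-controlled baseline. SAP 3.5.3 itself also defines the vital-sign baseline as the time-matched Day -1 value.

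**The concern.** A double difference should remove two things from a postdose reading: the participant's own predose level that day, and the change that time of day alone would produce. The second correction needs the untreated Day -1 profile. Step (2) in 3.5.3 uses the Day 1 profile, which is the quantity being assessed, so the Day 1 reading is subtracted from itself.

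Vital signs are a secondary endpoint. Protocol 2.2.2.1 reports mean heart-rate increases of 5 to 15 bpm across the doses given so far, so pulse rate over time is a known signal. A flat line with an ordinary-looking confidence interval could be taken as evidence of no effect, when the calculation could not have shown one.

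**Working it through.** **Inputs**

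- The three steps: SAP 3.5.3, with the contrasting step (2) in SAP 3.5.4.
- Times: Protocol Table 2 schedules triplicate supine vital signs at 0, 1, 2, 4, 8 and 12 h on Days -1, 1, 21, 35 and 56, which gives five postdose times.
- Parameters: systolic pressure, diastolic pressure and pulse rate (SAP 6.6.3).
- Groups: PF-06882961 (15 planned) and placebo (5 planned), Protocol 9.2.

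Let B(t), D1(t) and D56(t) be a participant's values at t hours on Days -1, 1 and 56. The plan states no figure to reproduce; the check is on the derivation rule.

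**Day 1, SAP 3.5.3 as written**

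1. Step (1): D1(t) - D1(0)
2. Step (2): D1(t) - B(0)
3. Step (3): [D1(t) - D1(0)] - [D1(t) - B(0)] = B(0) - D1(0)

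D1(t) cancels at every t. Reversing the order in step (3) changes only the sign.

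**Day 1, using the SAP 3.5.4 wording**

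[D1(t) - D1(0)] - [B(t) - B(0)], which keeps the postdose reading and corrects for time of day.

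**Extent**

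- Day 1 summary cells: 3 x 2 x 5 = 30.
- Distinct values with complete data: 3 x 2 = 6. Any variation over time in a group's mean would come only from missing readings.

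**Numerical check (assumed values, illustration only)**

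Fifteen participants were simulated with a pulse-rate residual SD of 3 bpm and Day 1 drug effects of 1, 3, 6, 5 and 2 bpm at 1, 2, 4, 8 and 12 h.

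| Rule | 1 h | 2 h | 4 h | 8 h | 12 h |
|---|---|---|---|---|---|
| 3.5.3 as written | -0.45 | -0.45 | -0.45 | -0.45 | -0.45 |
| 3.5.4 wording | 1.09 | 3.61 | 5.39 | 4.31 | -0.45 |

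The corrected 12 h mean is sampling error around the assumed 2 bpm; its match with the row above is chance. Adding 50 bpm to every Day 1 postdose value left the as-written result unchanged.

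**Day 56, if the same step (2) is applied**

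[D56(t) - D1(0)] - [D1(t) - B(0)] = [D56(t) - D1(t)] + [B(0) - D1(0)]

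This keeps the Day 56 reading but compares it with the profile after the first dose instead of the untreated one, so any Day 1 drug effect is subtracted. With assumed Day 56 effects of 7, 9, 12, 11 and 8 bpm, the as-written means were 4.08, 4.14, 5.25, 5.66 and 6.47. The 3.5.4 wording gave 5.63, 8.20, 11.10, 10.42 and 6.47.

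**How the empty Day 1 result would look**

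The flat line need not sit at zero. With independent errors of SD s, the as-written variance is 2s^2 and the 90% half-width is t(0.95, n-1) x sqrt(2) x s / sqrt(n). The documents give no s, so take 2 to 5 units:

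- n = 15: 1.761 x 1.414 x s / 3.873 = 1.29 (s = 2) to 3.22 (s = 5)
- n = 5: 2.132 x 1.414 x s / 2.236 = 2.70 (s = 2) to 6.74 (s = 5)

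Under the same assumption the 3.5.4 rule has variance 4s^2. The as-written interval is then sqrt(2)/2 = 0.71 times as wide, or 29% narrower.

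**The case against.** The strongest reply is that this is a typing error that nobody would program. SAP 3.5.3 has just defined baseline as the Day -1 value. The word *other* in step (2) makes sense only if both values come from the same day. Read literally on Day 1, step (3) would match each reading to itself. The ECG rule shows the intended form. That is persuasive about intent, but SAP 6.6.3 sends the programmer to Section 3.5.3, and no text overrides its wording. A silent correction would leave the analysis run different from the analysis specified. A lost minus sign in the copy reviewed cannot be fully excluded, but the other mentions of Day -1 in the same section kept theirs.

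The second reply is that little is lost. The output is supplementary and descriptive, in a study with no hypotheses. The intended quantity equals [D1(t) - B(t)] - [D1(0) - B(0)]. With complete data, its mean can be recovered from the mean changes from time-matched baseline at t and at 0 h, if the Day 1 0 h change is tabulated. This stands and limits the seriousness. The confidence interval cannot be recovered from those means.

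The third reply concerns apparent precision, and it also stands. The 29% figure needs independent errors. If readings on one day share a shift with variance v, and residual variance is e, the as-written variance is 2v + 2e against 4e for the 3.5.4 rule. The SD ratio is sqrt((1 + v/e)/2): 0.71 at v = 0, 1.00 at v = e and 1.22 at v = 2e. The direction can therefore reverse, and the conclusion does not use this figure.

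**Conclusion.** The concern holds: SAP 3.5.3 step (2) is wrong as written and should be fixed. Applied literally, it makes all 30 Day 1 double-difference cells, and the Day 1 plots, functions of two pretreatment readings only. This follows from the algebra for any drug effect and needs no assumed effect size or SD. The Day 56 vital-sign plot would also use the wrong comparator if the same step is applied there.

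The damage is confined to the double-difference form of blood pressure and pulse rate. Absolute values, changes from time-matched baseline and the categorical summaries are correctly defined. So is the ECG heart-rate double difference, which is scheduled at the same times. The primary PK endpoints are untouched.

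**What to change.** In SAP 3.5.3 step (2), replace the final Day 1 with Day -1, so that the step agrees with SAP 3.5.4. The same edit restores the untreated comparator for the Day 56 plot.

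The cost is one character in the SAP. Day -1 and Day 1 vital signs are already scheduled at the same nominal times, so no new data, visits or change to the design are needed. If the outputs have already been programmed, check which version of step (2) was used.
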